[Part 2 of 2 of the document. The other parts are not shown.]

- Study participants who failed Screening (eg, due to transient out-of-range safety laboratory values or in the Investigator's judgment mild acute illness, eg, a cold) may be rescreened after complete recovery of the mild acute illness and/or normalization of the out-of-range safety laboratory values.
- Study participants with LTB infection, indicated by positive PPD skin test or positive IGRA test result (or TB questionnaire indicating an increased risk of exposure or infection with TB for study participants ages 2 to 4 years with documented BCG vaccination) and a chest imaging without evidence of TB infection at Screening, may be rescreened after initiation of treatment for latent TB. Prior to first study medication administration, TB treatment must have been ongoing for at least 4 weeks before enrollment will be allowed and after approval of the Medical Monitor. Treatment for TB must be continued until completion of 9 months of therapy (refer to Section 10.7.9).
- Rescreening might be allowed more than once but not in case of repeated occurrence of the same illness. All Screening assessments must be repeated as applicable in case of Rescreening. The maximum duration of the Rescreening Period is 28 days or 4 weeks. Rescreening must only be scheduled after an appropriate time period after the initial Screening Visit allowing for repetition of blood collection (depending on local requirements for maximum blood volumes; depending on study participant weight).
- All study participants who failed to be enrolled within the Screening Period of 28 days must be registered as Screen Failure in the interactive voice/web response system (IXRS). Study participants approved to be rescreened must be registered with a new study participant number.

Change #47

Section 6.4 Withdrawal criteria, the third withdrawal criterion:

3. Study participant develops confirmed latent or active TB once enrolled or discontinues treatment for latent TB prematurely or is noncompliant with anti-TB therapy in the Investigator's or Sponsor's opinion must discontinue further use of study medication and be immediately withdrawn from study participation (see Section 10.7.9).

Has been changed to:

3. Study participant who develops confirmed reactivation of latent or active TB or NTMB infection during the study (including, but not limited to, conversion demonstrated by IGRA or PPD or other diagnostic means, eg, TB questionnaire, during the course of the study) must be withdrawn.

Change #48

Section 6.4 Withdrawal criteria, a new withdrawal criterion has been added below withdrawal criterion 3, and subsequent criteria have been renumbered:

4. Study participant who prematurely discontinues treatment for LTB, or, in the opinion of the Investigator or Sponsor, is noncompliant with anti-TB therapy must be withdrawn.

Change #49

Section 7.2 Treatments to be administered, fourth paragraph, the last sentence:

In addition, study participants will have the option to either switch to home-based CZP injection or switch back to administration at the study site at anytime during the study.

Has been changed to:

In addition, if needed, home dosing can be performed by qualified health care professionals according to the written instructions for the correct sc injection technique provided by the site staff. Study participants will have the option to either switch to home-based CZP injection or switch back to administration at the study site at anytime during the study.

Change #50

Section 7.2 Treatments to be administered, the fifth paragraph:

The method of injection (ie, qualified site personnel-injection at study site; injection by the study participant/caregiver at the study site or at home) and the site of injection (abdomen, thigh) will be recorded in the CRF at each visit.

Has been changed to:

The method of injection (ie, qualified site personnel-injection at study site; injection by the study participant/caregiver or qualified health care professional at the study site or at home) and the site of injection (abdomen, thigh) will be recorded in the CRF at each visit.

Change #51

Section 7.4 Labeling, second paragraph, the third sentence:

The tear-off section will be removed and attached to the CRF at the time of study medication administration to the study participant and the main section will remain affixed to the individual container.

Has been changed to:

The tear-off section will be removed and attached to the source document at the time of study medication administration to the study participant and the main section will remain affixed to the individual container.

Change #52

Section 7.8.1 Permitted concomitant treatments (medications and therapies), the first bullet:

- MTX, if being used:
 - Must have been stable for at least 1 month before Screening (Visit 1) at ≥ 10 to $\leq 15\text{mg/m}^2$ per week.
 - The maximum dose allowed during the study is 15mg/m^2 per week.
 - Prior to Week 16, route of administration must not change. After Week 16, the route of administration may be changed.
 - During the study, the MTX dose may be decreased, but not discontinued (except for documented reasons of intolerance or toxicity, or in association with study participants achieving CRM and after CZP was discontinued).
 - After discontinuation, MTX treatment can be restarted.

Has been changed to:

- MTX, if being used:
 - Must have been stable for at least 1 month before Screening (Visit 1) at ≥ 10 to $\leq 15\text{mg/m}^2$ per week.
 - During the study, an increase is allowed only after Week 16 and to a maximum dose of 15mg/m^2 per week.
 - Prior to Week 16, route of administration must not change. After Week 16, the route of administration may be changed.
 - During the study, the MTX dose may be decreased, but not discontinued. Methotrexate may be discontinued only for documented reasons of intolerance or toxicity, or in study participants who achieve CRM and only after discontinuation of CZP.
 - Study participants who do not achieve persistent CRM status can reinitiate therapy with MTX.

Change #53

Section 7.8.1 Permitted concomitant treatments (medications and therapies), the fifth bullet:

- Corticosteroids:
 - At study entry, the dose should have been stable for at least 7 days prior to the Baseline joint examination at a maximum dose of 10mg or 0.2mg/kg prednisone (or equivalent) per day, whichever is the smaller dose.

- During the study, the dose of oral corticosteroids may be decreased but not initiated or increased above 10mg or 0.2mg/kg prednisone (or equivalent) per day, whichever is the smaller dose. The dose must be stable in the 7 days prior to a joint examination.
- Intra-articular (ia) corticosteroids may be administered no more frequently than every 4 months and no more than up to 3 times in 1 year and only into up to 3 joints at a single time point.
- If 1 or more joints have been injected (limited to 3 joints at a single time point), this/these joint(s) must be excluded from the PRINTO/PRCSG standard joint examination.
- Intravenous (iv) corticosteroid use is permitted only for stress dosing for the purposes of surgery.

Has been changed to:

- Corticosteroids:
 - At study entry, the dose should have been stable for at least 7 days prior to the Baseline joint examination at a maximum dose of 10mg or 0.2mg/kg prednisone (or equivalent) per day, whichever is the smaller dose.
 - During the study, the dose of oral corticosteroids may be decreased but not initiated or increased above 10mg or 0.2mg/kg prednisone (or equivalent) per day, whichever is the smaller dose. The dose must be stable in the 7 days prior to a joint examination.
 - Initiation of topical corticosteroids is allowed for treatment of uveitis if developed during the course of the study.
 - Intra-articular (ia) corticosteroids may be administered no more frequently than every 4 months and no more than up to 3 times in 1 year and only into up to 2 joints at a single time point.
 - Any joint injected with ia corticosteroids will be excluded from the efficacy analysis for a period of 3 months.
 - Intravenous (iv) corticosteroid use is permitted only for stress dosing for the purposes of surgery.

Change #54

Section 7.8.2 Rescue medication, the fourth and fifth paragraphs:

The following medications are defined as rescue medication in the first 16 weeks of this study:

- Initiation of MTX (if not being used at study entry), or increase of MTX above Baseline.
- Initiation of oral corticosteroids, or increase of oral corticosteroids above Baseline.
- Injection of intra-articular (ia) corticosteroids into more than 3 joints at a single time point.

- Injection of intra-articular (ia) corticosteroids into the same joint more frequently than 3 times in a 12-month period.
- Intravenous (iv) corticosteroids (any dose), if not used for stress dosing for the purposes of surgery.
- Intramuscular (im) corticosteroids.

The following medications are defined as rescue medication for the remainder of the study:

- Initiation of MTX (if not being used at study entry), and increase of MTX above 15mg/m² per week at any time.
- Initiation of oral corticosteroids, or increase to >10mg or 0.2mg/kg (whichever is the smaller dose).
- Injection of intra-articular (ia) corticosteroids into more than 3 joints at a single time point.
- Injection of intra-articular (ia) corticosteroids into the same joint more frequently than 3 times in a 12-month period.
- Intravenous (iv) corticosteroids (any dose), if not used for stress dosing for the purposes of surgery.
- Intramuscular corticosteroids (im).

Have been changed to:

The following medications are defined as rescue medication in the first 16 weeks of this study:

- Initiation of MTX (if not being used at study entry), or increase of MTX above Baseline.
- Initiation of oral corticosteroids, or increase above Baseline.

The following medications are defined as rescue medication after Week 16:

- Initiation of MTX (if not being used at study entry), and increase of MTX above 15mg/m² per week at any time.
- Initiation of oral corticosteroids, or increase to >10mg or 0.2mg/kg prednisone (or equivalent) per day, whichever is the smaller dose.

The following medications are defined as rescue medication when given at any time during the study:

- Injection of intra-articular (ia) corticosteroids into more than 2 joints at a single time point.
- Injection of intra-articular (ia) corticosteroids into the same joint more frequently than 3 times in a 12-month period.
- Intravenous (iv) corticosteroids (any dose), if not used for stress dosing for the purposes of surgery.

- Intramuscular (im) corticosteroids.

Change #55

Section 7.9 Enrollment and numbering of study participants, the second sentence:

The IVRS will provide the Investigator with the unique study participant number assigned to each study participant.

Has been changed to:

The Investigator will enter the unique study participant number assigned to each study participant, based on a predefined range of study participant numbers assigned to the Investigator's site.

Change #56

Section 8.1 Visit 1 (Week -4 to 0) Screening, the tenth bullet has been moved below the bullet "TB screening":

- TB questionnaire

Change #57

Section 8.1 Visit 1 (Week -4 to 0) Screening, a new bullet has been added above the 15th bullet "TB screening":

- Chest x-ray (only for study participants with positive IGRA or PPD testing)**

Change #58

Section 8.1 Visit 1 (Week -4 to 0) Screening, the 15th bullet:

- TB screening if not performed within 3 months of Screening: PPD skin test (or QuantiFERON required to be performed by the central lab if the study participant has a documented history of severe positive PPD reaction or a documented history of BCG vaccination)

Has been changed to:

- TB screening if not performed within 3 months of Screening: PPD skin test for study participants from 2 to 4 years of age (unless written documentation for BCG vaccination is available) or IGRA (to be performed by the central lab) for study participants from 5 to 17 years of age)**

Change #59

Section 8.1 Visit 1 (Week -4 to 0) Screening, the last bullet:

- IVRS phone call (to receive study participant number assignments)

Has been changed to:

- IXRS contact (to register study participant with unique study participant number)

Change #60

Section 8.1 Visit 1 (Week -4 to 0) Screening, the note at the end of the section:

*Change in height and weight over the last 6 months and over the last year will be collected via parent-/self-report, if available from medical records.

Has been changed to:

*Change in height and weight over the last 6 months and over the last year will be collected via parent-/self-report, if not available from medical records.

Change #61

Section 8.1 Visit 1 (Week -4 to 0) Screening, a new note has been added at the end of the section for chest x-ray, TB screening, and TB questionnaire:

**For details of TB screening and testing, see Section 10.7.9.

Change #62

Section 8.2 Visit 2 (Week 0) Baseline, the 19th and 20th bullets:

- FPS-R for study participants ages 5 to 11 years (at Baseline and daily assessment during the first 7 days of treatment)
- JIA Pain VAS for study participants ages 12 to 17 years; acute and standard versions (both at Baseline and daily assessment of the acute version during the first 7 days of treatment)

Has been changed to:

- FPS-R for study participants ages 5 to 11 years (at Baseline and daily assessment on Day 1 to Day 7)
- JIA Pain VAS for study participants ages 12 to 17 years; acute and standard versions (both at Baseline and daily assessment of the acute version on Day 1 to Day 7)

Change #63

Section 8.2 Visit 2 (Week 0) Baseline, the paragraph at the end of the section:

Documentation of the assessment of all 6 core set measures of PedACR response (PRINTo/PRCSG standard joint examination, Physician's Global Assessment of Disease Activity [VAS], CHAQ-parent reported, Parent's Assessment of Arthritis Pain [VAS], Parent's Global Assessment of Overall Well-Being [VAS] and DMS) **will be submitted to UCB or designee for immediate review of completeness, while the study participant is still on site.**

Has been changed to:

Documentation of the assessment of all 6 core set measures of PedACR response (PRINTo/PRCSG standard joint examination, Physician's Global Assessment of Disease Activity [VAS], CHAQ-parent reported, Parent's Assessment of Arthritis Pain [VAS], Parent's Global Assessment of Overall Well-Being [VAS] and CRP) **will be submitted to**

UCB or designee for immediate review of completeness, while the study participant is still on site.

Change #64

Section 8.3 Visits 3 and 4 (Weeks 1 and 2), the ninth bullet:

- Collection of JIA Pain VAS or FPS-R completed during the first 7 days of treatment

Has been changed to:

- Collection of JIA Pain VAS or FPS-R completed on Day 1 to Day 7

Change #65

Section 8.4 Visits 5 to 10 (Weeks 4, 8, 12, 16, 20, and 24), the paragraph at the end of the section:

Documentation of the **Week 16** assessment of all 6 core set measures of PedACR response (PRINTO/PRCSG standard joint examination, Physician's Global Assessment of Disease Activity [VAS], CHAQ-parent reported, Parent's Assessment of Arthritis Pain [VAS], Parent's Global Assessment of Overall Well-Being [VAS] and DMS) **will be submitted to UCB or designee for immediate review of completeness, while the study participant is still on site.**

Has been changed to:

Documentation of the **Week 16 and Week 24** assessment of all 6 core set measures of PedACR response (PRINTO/PRCSG standard joint examination, Physician's Global Assessment of Disease Activity [VAS], CHAQ-parent reported, Parent's Assessment of Arthritis Pain [VAS], Parent's Global Assessment of Overall Well-Being [VAS] and CRP) **will be submitted to UCB or designee for immediate review of completeness, while the study participant is still on site.**

Change #66

Section 8.5 Visits 11 and continuing (Week 32 and every 8 weeks thereafter), the eleventh bullet has been removed:

- TB screening is to be repeated every 48 weeks in those study participants with a negative TB test at their most recent assessment. A PPD skin test must be performed. (QuantIFERON required to be performed by the central lab if the study participant has a documented history of severe positive PPD reaction or a documented history of BCG vaccination) (Week 48 and every 48 weeks thereafter).

Change #67

Section 8.5 Visits 11 and continuing (Week 32 and every 8 weeks thereafter), the paragraph at the end of the section:

Documentation of the **Week 56** assessment of all 6 core set measures of PedACR response (PRINTO/PRCSG standard joint examination, Physician's Global Assessment of Disease Activity [VAS], CHAQ-parent reported, Parent's Assessment of Arthritis Pain [VAS], Parent's Global Assessment of Overall Well-Being [VAS] and DMS) **will be submitted to**

UCB or designee for immediate review of completeness, while the study participant is still on site.

Has been changed to:

Documentation of the **Week 56** assessment of all 6 core set measures of PedACR response (PRINTO/PRCSG standard joint examination, Physician's Global Assessment of Disease Activity [VAS], CHAQ-parent reported, Parent's Assessment of Arthritis Pain [VAS], Parent's Global Assessment of Overall Well-Being [VAS] and CRP) **will be submitted to UCB or designee for immediate review of completeness, while the study participant is still on site.**

Change #68

Section 9 Assessment of pharmacokinetics and immunological variables, the third, fourth, and fifth paragraphs:

Once at least 20 study participants (minimum 6 study participants in each age group: 2 to 5 years, 6 to 11 years, and 12 to 17 years) have completed Week 12 (Visit 7), PK data will be compared with plasma concentrations observed previously in adult study participants with RA.

This CZP plasma concentration analysis may be done in 2 or 3 stages if at least 20 study participants in total complete Week 12 (Visit 7) before 6 study participants in 1 or both of the other age groups have completed. The plasma concentration analysis would be performed on the available completed study participants in the first stage. The analysis would then be performed on the other age groups once the required minimum number of 6 study participants have completed Week 12 (Visit 7).

If plasma concentrations are not consistent with those observed in previous studies with adults, the dosing algorithm may be changed via a protocol amendment. This study will continue during the PK analysis. All study participants assessed in this analysis will continue treatment after Week 12 (Visit 7).

Have been changed to:

Plasma concentration data for CZP from this study will be compared with plasma concentrations observed previously in adult study participants with RA, as described in Section 13.7. This plasma concentration analysis will be done on an ongoing basis throughout the study, starting when 6 study participants in 1 of the age groups have completed Week 12 (Visit 7).

Interim CZP plasma concentration data available at the time of Protocol Amendment 3 indicate that no change to the dosing algorithm is required. If future analyses indicate that plasma concentrations are outside of the exposure range of those observed in previous studies with adults, the dosing algorithm may be changed via a protocol amendment, and if necessary additional interim analyses including PopPK, may be performed. This study will continue during the PK analysis. All study participants assessed in this analysis will continue treatment after Week 12 (Visit 7).

Change #69

Section 9 Assessment of pharmacokinetics and immunological variables, the following sentence has been added below the fourth paragraph:

The final pediatric PopPK model will be combined with PD data (PedACR) and if the data allow, an exposure-response relationship will be derived.

Change #70

Section 9 Assessment of pharmacokinetics and immunological variables, the following has been added at the end of the section:

These plasma samples may be used additionally for analyses of CZP and its constituent moieties using alternative assay methods. The results of the analyses of CZP and its constituent moieties from alternative methods may be reported separately.

Change #71

Section 10.1.8 Ongoing safety data review and oversight, second paragraph, the fourth and fifth sentences:

In addition, there will be a study-specific Safety Review Committee consisting of the UCB study physician, the UCB study GCSP representative, and an external pediatric rheumatologist experienced in the field and clinical studies in pediatrics and familiar with safety issues in this population. A charter will be developed to address the logistics of such a committee.

Has been changed to:

In addition, a Data and Safety Monitoring Board (DSMB) will periodically review all emerging safety data (see Section 13.7). The DSMB will function and meet on a regular basis as per the agreed upon charter.

Change #72

Section 10.1.8 Ongoing safety data review and oversight, the last sentence:

The Sponsor Study Physician or medically qualified designee/equivalent will conduct an ongoing review of SAEs and perform ongoing SAE reconciliations in collaboration with the GCSP representative.

Has been changed to:

The Sponsor Study Physician or medically qualified designee/equivalent will conduct an ongoing review of SAEs and perform ongoing SAE reconciliations in collaboration with the Drug Safety and Data Management representatives.

Change #73

Section 10.3 AEs of special interest:

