Rescue medication use is defined as any initiation of treatment or increase in dose of a medication used to treat JIA (in addition to the IMP) that is considered to impact the efficacy analyses. A study participant requiring rescue medication after first administration of IMP is considered as a treatment failure from that time point forward for the purpose of efficacy analyses.

Has been changed to:

Rescue medication use is defined as any initiation of treatment or increase in dose of a medication used to treat JIA (in addition to the IMP) that is considered to impact the efficacy analyses. A study participant requiring rescue medication after first administration of IMP is considered as a treatment failure from that time point forward for the purpose of efficacy analyses. Exception: A study participant initiating rescue medication use after the Week 56 visit will not be considered a treatment failure and the efficacy data will be analyzed as observed without imputation.

Change #5

Section 8.5 Visits 11 and continuing (Week 32 and every 8 weeks thereafter), a new bullet has been added as sixth bullet:

- TB screening once a year (approximately every 48 weeks)

Change #6

Section 10.1 Adverse events, the following section has been added:

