Data collected after the taking of rescue medication will be treated as missing for continuous efficacy endpoints and non-response for binary efficacy endpoints in all analyses except where specifically stated otherwise. See Section 7.8.2 for a list of medications which would result in data at only the next scheduled visit (and not all subsequent visits) being treated as missing/non-response. These data will then be imputed as for any other missing data. The exception is any rescue medication use that is initiated after Week 56: Per Protocol Amendment 7, efficacy data after any rescue medication use initiated after Week 56 will not be imputed (as nonresponse or missing) and will be analyzed as observed.

Change #19

Section 16 REFERENCES, the following publication has been added:

17.18 Protocol Amendment 8

Rationale for the amendment

The primary purpose of this substantial amendment is to reduce the study participants' burden by limiting the frequency of on-site visits, safety sampling, and efficacy assessments.

The frequency of on-site visits will be reduced from every 8 weeks to every 16 weeks in this long-term study. At the time of implementing Protocol Amendment 8, all ongoing study participants have at least completed the visit for Week 180. As before, on-site CZP administration between scheduled visits is offered as needed.

The frequency of safety sampling (blood sampling and urinalysis) will be extended from every 8 weeks to every 16 weeks to reduce study participants' burden in line with the updated on-site CZP administration schedule. Safety data collected previously during the study and close evaluation by the DSMB support the extension of sampling frequency.

This longer interval will also be implemented for efficacy assessments to further reduce the study participants' burden and will be appropriate to describe the long-term efficacy of CZP.

In addition, blood samples to determine CZP plasma concentrations and anti-CZP antibodies will no longer be collected in the study to further reduce study participants' burden.

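### Excluding injected joints from the efficacy analysis for 3 months is informative and can flatter the joint-count components of PedACR and JADAS

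*Protocol*

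**What the plan says.** The latest wording available for Section 7.8.1 is the replacement text of Change #53 in the Amendment 3 log. The only later listed edits to that section concern methotrexate (Amendment 5, Change #19).

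- **Permitted injections.** At most two joints may be injected per session, and the limit on sessions is "no more frequently than every 4 months and no more than up to 3 times in 1 year".
- **Analysis rule.** "Any joint injected with ia corticosteroids will be excluded from the efficacy analysis for a period of 3 months". The text does not say whether the joint also leaves the Baseline count, or what status it has while excluded.
- **Rescue (Section 7.8.2, Change #54).** At any time, "Injection of intra-articular (ia) corticosteroids into more than 2 joints at a single time point" is rescue, as is injecting the same joint more than three times in 12 months. One or two joints at a session are not on the list shown. In the first 16 weeks, starting methotrexate or oral corticosteroid, or raising either above Baseline, is rescue.
- **Consequence of rescue.** Section 7.8.2 (Amendment 7, Change #4): "A study participant requiring rescue medication after first administration of IMP is considered as a treatment failure from that time point forward". Section 13.6 (Amendment 7, Change #18) treats later data as "non-response for binary efficacy endpoints in all analyses except where specifically stated otherwise". Both exempt rescue begun after Week 56.
- **A further rule in Section 13.6.** "See Section 7.8.2 for a list of medications which would result in data at only the next scheduled visit". The text at hand does not identify those medications.

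**The concern.** Two kinds of treatment escalation are handled differently. A systemic increase before Week 16 makes the participant a non-responder. A steroid injection into one or two joints does not do so on the list shown, and the injected joints leave the analysis for 3 months. Those joints are presumably the ones responding least, so the missing data are not neutral: a local failure becomes an absent observation.

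The joint examination feeds PedACR, and the active joint count enters JADAS directly (Section 11.9). At stake is whether joint-count improvement by dose regimen is overstated, most of all in children with few active joints. Because Baseline handling is not fixed in the text at hand, two analysts could also reach different counts from the same data.

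**Working it through.** The protocol states no figure for the effect of this rule, so there is none to reproduce.

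**Inputs**
- k, joints injected at one session without rescue: at most 2 (Section 7.8.1).
- Exclusion of 3 months and at least 4 months between sessions (read as per participant). Windows therefore do not overlap and at most 2 joints are out at once. Three sessions a year give up to 3 × 3 = 9 months of exclusion in 12.
- A, active joints at Baseline: not in the part at hand. Assumed; 3 to 30 was examined.
- r, other joints that have resolved by follow-up (net, r ≥ 0).
- Share of participants injected: not given, and no assumption is made.

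**Apparent improvement in the active count**, for injected joints active at Baseline and before injection:
- held at pre-injection status: r/A
- removed from follow-up only: (r + k)/A
- removed from Baseline and follow-up: r/(A − k)

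For r ≥ 0 the second exceeds the first by k/A, and the third is never below the first.

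**No other joint changes (r = 0, k = 2)**

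| A | Held | Follow-up only | Both sides |
|---|---|---|---|
| 3 | 0% | 66.7% | 0% |
| 4 | 0% | 50.0% | 0% |
| 5 | 0% | 40.0% | 0% |
| 6 | 0% | 33.3% | 0% |
| 7 | 0% | 28.6% | 0% |
| 10 | 0% | 20.0% | 0% |
| 20 | 0% | 10.0% | 0% |

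Under follow-up-only removal, 30% is reached only for A ≤ 6 and 50% only for A ≤ 4. With k = 1, within the assumed range, 30% is reached only at A = 3 (1/3 = 33.3%; 1/4 = 25%).

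**Some other joints improve, both-sides removal (k = 2)**
- 2/8 = 25.0% becomes 2/6 = 33.3%
- 3/12 = 25.0% becomes 3/10 = 30.0%
- 4/10 = 40.0% becomes 4/8 = 50.0%

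**JADAS.** The active count enters on a 0 to 71 scale and change from Baseline is assessed. Follow-up-only removal lowers the score by up to 2 points. Both-sides removal leaves the change as it was: (A − r − 2) − (A − 2) = −r.

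**Timing.** Three months is about 13 weeks. An injection just after Week 4 would exclude the joints until about Week 17, covering Week 12 and Week 16.

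**Scale of the response rates.** Section 1 (Amendment 9, Change #7) gives Week 12 PedACR30 of 77.3% in 163 participants and 75.6% on the original regimen. 0.773 × 163 ≈ 126. Taking 78 on the original regimen, 0.756 × 78 ≈ 59. That leaves 67 of 85 (78.8%) on the reduced regimen. One reclassified responder there moves the rate by 1/85 = 1.2 points. Going below 50% would take 25: (67 − 25)/85 = 49.4%, against (67 − 24)/85 = 50.6%.

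**The case against.** The strongest defence is that exclusion keeps the steroid's effect from being credited to certolizumab pegol. Take 8 active joints, 2 injected and resolved, and 2 others resolved. As-observed scoring gives 4/8 = 50%; exclusion from both sides gives 2/6 = 33%. Against as-observed scoring, the rule is therefore conservative. This stands, but it does not favour exclusion over holding the joint at its pre-injection status, which gives 2/8 = 25% and also withholds credit for the steroid.

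A reader might infer that the rule can produce a PedACR response with no drug effect at all. The documents do not support that. An artefact with no other change requires the joint to leave follow-up but stay in Baseline, which the text does not say. PedACR has six core measures; Section 8.4 (Amendment 9, Change #83) lists the joint examination beside physician global, CHAQ, parent pain, parent global and CRP. Dropping a joint does not alter those other five. How many measures must improve is in Section 11.1, which was not in the part at hand. If three must improve (an assumption), two joint counts alone cannot create a responder.

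Three further limits stand. Permitted injections may be on the next-visit list that Section 13.6 attributes to Section 7.8.2; if so, the next visit is already non-response or missing. At most two joints are out at once. Baseline handling may be settled in sections not shown or in a statistical analysis plan. None of this makes exclusion neutral: the protocol itself fixes the 3-month removal.

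**Conclusion.** The point holds for the joint-count components. Compared with holding injected joints at their pre-injection status, exclusion can raise apparent improvement and, where the other joints are stable or better, does not lower it. With two joints out, the active count falls by 40% at 5 assumed Baseline joints and 33% at 6 if removal is from follow-up only. If removal is from both sides, the artefact is zero when nothing else changes but can carry a borderline result across a threshold, as in 25% to 33%.

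This rests on assumed Baseline counts, on injected joints being those doing badly, and on the text shown being current. The figures are changes in one joint count, not PedACR response rates, and the frequency of injection is unknown. A reader might also infer that the futility result is in doubt. That cannot be shown: the decision used Week 16 data whose count is not given, and the Week 12 back-calculation would need 25 reclassified responders on the reduced regimen. Efficacy is the secondary objective, and Section 13.7 calls the data presentations descriptive. The change is worth making, but the point does not undermine the trial's primary objectives.

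**What to change.** Replace the exclusion sentence with an analysis rule along these lines:

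> For PedACR and JADAS, a joint injected with intra-articular corticosteroid remains in the Baseline count. For 3 months after injection it is carried in post-Baseline counts at its last status before injection (active, limited in motion). A sensitivity table repeats the analysis with the same joints removed from both Baseline and follow-up.

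Do not extend this to the determination of clinically inactive disease. Six months of continuous inactive disease defines clinical remission on medication, which governs stopping certolizumab pegol and methotrexate (Section 7.2; Section 7.8.1). Forcing a joint to active there would alter a treatment rule, so that determination stays as it is. Who may be injected, and what counts as rescue, also stay unchanged.

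The cost is this analysis text and one table, provided injected joints and dates are recorded. Response rates may fall slightly. If the Week 24 interim already reported used exclusion, later results on the new basis will not be directly comparable; the sensitivity table helps bridge them if that interim also removed the joints from both sides.
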